11.2. Table of Contents for Data Display Specifications

11.2.1. Output Tables

Table 9: List of Output Tables

Title	Population	Programming notes
Study Population		
14.1.1.1 Subject Disposition	Screened	Include three sections: screened, run-in, randomized
14.1.1.2 Subject Randomization by Country and Investigator	Randomized	
14.1.2.1 Major Protocol Deviations	FAS	
14.1.2.2 Reasons for Exclusion from Analysis Sets	Randomized	
14.1.3.1 Subject Demographic and Baseline Characteristics	SAF	
14.1.3.2 Subject Demographic and Baseline Characteristics	SAF-Orth	
14.1.3.3 Subject Demographic and Baseline Characteristics	FAS	
14.1.3.4 Subject Demographic and Baseline Characteristics	FAS-I	
14.1.3.5 Subject Demographic and Baseline Characteristics	PPS	

Title	Population	Programming notes
14.1.3.6 Subject Demographic and Baseline Characteristics	PPS-I	
14.1.3.7 Subject Demographic and Baseline Characteristics	SAF-UDS	
14.1.3.8 Subject Demographic and Baseline Characteristics	UES	
14.1.3.9 Other Baseline Characteristics	FAS	
14.1.3.10 Other Baseline Characteristics	FAS-I	
14.1.3.11 Other Baseline Characteristics	PPS	
14.1.3.12 Other Baseline Characteristics	PPS-I	
14.1.4 Medical History	SAF	
14.1.5.1 Prior Non-Overactive-Bladder (OAB) Medication	SAF	
14.1.5.2 Prior Overactive Bladder (OAB) Medication	SAF	
14.1.6.1 Treatment Exposure	SAF	Double-blind period
14.1.6.2 Treatment Exposure	FAS	Double-blind period
14.1.6.3 Treatment Compliance Double-Blind Period	SAF	
14.1.6.4 Treatment Compliance Double-Blind Period	FAS	
14.1.7.1 COVID-19 Impact	SAF	

Title	Population	Programming notes	
Efficacy Endpoints			
Co-Primary Endpoints			
14.2.1.1	Average Number of Daily Micturition Episodes	FAS	Descriptive statistics, include CFB
14.2.1.2	Change from Baseline in Average Number of Daily Micturition Episodes Primary Efficacy Analysis (MMRM)	FAS	Include all intervals but Week 12 in the front
14.2.1.3	Change from Baseline at Week 12 in Average Number of Daily Micturition Episodes Primary Efficacy Sensitivity Analysis (ANCOVA with MI)	FAS	
14.2.1.4	Change from Baseline in Average Number of Daily Micturition Episodes Primary Efficacy Analysis	PPS	Descriptive statistics, include CFB
14.2.1.5	Change from Baseline at Week 12 in Average Number of Daily Micturition Episodes Primary Efficacy Sensitivity Analysis (ANCOVA with MI)	PPS	Include all intervals but Week 12 in the front
14.2.1.6	Average Number of Daily Micturition Episodes by Subgroup	FAS	Descriptive statistics, include CFB
14.2.1.7	Change from Baseline in Average Number of Daily Micturition Episodes Primary Efficacy Analysis (MMRM) by Subgroup	FAS	Include all intervals but Week 12 in the front
14.2.2.1	Average Number of Daily Urgency Episodes	FAS	Descriptive statistics, include CFB

Title	Population	Programming notes
14.2.2.2 Change from Baseline in Average Number of Daily Urgency Episodes Primary Efficacy Analysis (MMRM)	FAS	Include all intervals but Week 12 in the front
14.2.2.3 Change from Baseline at Week 12 in Average Number of Daily Urgency Episodes Primary Efficacy Sensitivity Analysis (ANCOVA with MI)	FAS	
14.2.2.4 Change from Baseline in Average Number of Daily Urgency Episodes Primary Efficacy Analysis (MMRM)	PPS	Include all intervals but Week 12 in the front
14.2.2.5 Change from Baseline in Average Number of Daily Urgency Episodes Primary Efficacy Sensitivity Analysis (ANCOVA with MI)	PPS	Include all intervals but Week 12 in the front
14.2.2.6 Average Number of Daily Urgency Episodes by Subgroup	FAS	Descriptive statistics, include CFB
14.2.2.7 Change from Baseline in Average Number of Daily Urgency Episodes Primary Efficacy Analysis (MMRM) by Subgroup	FAS	Include all intervals but Week 12 in the front
Secondary Efficacy Endpoints		
14.2.3.1 Average Number of Nocturia Episodes per Day	FAS	Descriptive statistics, include CFB
14.2.3.2 Change from Baseline in Average Number of Nocturia Episodes per Day (MMRM)	FAS	Include all intervals but Week 12 in the front

Title	Population	Programming notes
14.2.3.3 Change from Baseline in Average Number of Nocturia Episodes per Day (MMRM)	PPS	Include all intervals but Week 12 in the front
14.2.4.1 Average Number of Daily Urge Urinary incontinence Episodes	FAS-I	Descriptive statistics, include CFB
14.2.4.2 Change from Baseline in Average Number of Daily Urge Urinary incontinence Episodes (MMRM)	FAS-I	Include all intervals but Week 12 in the front
14.2.4.3 Change from Baseline in Average Number of Daily Urge Urinary incontinence Episodes (MMRM)	PPS-I	Include all intervals but Week 12 in the front
14.2.5.1 International Prostate Symptom Score (IPSS) Storage Score	FAS	Descriptive statistics, include CFB
14.2.5.2 Change from Baseline in International Prostate Symptom Score (IPSS) Storage Score (MMRM)	FAS	Include all intervals but Week 12 in the front
14.2.5.3 Change from Baseline in International Prostate Symptom Score (IPSS) Storage Score (MMRM)	PPS	Include all intervals but Week 12 in the front
14.2.6.1 Average Volume Voided per Micturition	FAS	Descriptive statistics, include CFB
14.2.6.2 Change from Baseline in Average Volume Voided per Micturition (MMRM)	FAS	Include all intervals but Week 12 in the front
14.2.6.3 Change from Baseline in Average Volume Voided per Micturition (MMRM)	PPS	Include all intervals but Week 12 in the front

Title	Population	Programming notes
Other Efficacy and PROs Endpoints		
14.2.7.1 International Prostate Symptom Score (IPSS) Quality of Life Score	FAS	Descriptive statistics, include CFB
14.2.7.2 International Prostate Symptom Score (IPSS) Voiding Score	FAS	Descriptive statistics, include CFB
14.2.8.1 Urgency Episodes per Day 50% Responder Analysis (CMH)	FAS	Descriptive statistics
14.2.9.1 Change from Baseline in Average Number of Total Incontinence Episodes per Day	FAS-I	Descriptive statistics, include CFB
14.2.9.2 Urge Urinary Incontinence Episodes per Day 75% Responder Analysis (CMH)	FAS-I	Descriptive statistics
14.2.10.1 Symptom Bother Score as Assessed by [REDACTED] (1-week recall)	FAS	Descriptive statistics, include CFB
14.2.10.2 Health-Related Quality of Life (HQOL) Subscale Coping Score as Assessed by [REDACTED] (1-week recall)	FAS	Descriptive statistics, include CFB
14.2.10.3 Health-Related Quality of Life (HQOL) Subscale Concern Score as Assessed by [REDACTED] (1-week recall)	FAS	Descriptive statistics, include CFB

Title	Population	Programming notes
14.2.10.4 Health-Related Quality of Life (HROL) Subscale Sleep Score as Assessed by [REDACTED] (1-week recall)	FAS	Descriptive statistics, include CFB
14.2.10.5 Health-Related Quality of Life (HRQL) Subscale Social Interaction Score as Assessed by [REDACTED] (1-week recall)	FAS	Descriptive statistics, include CFB
14.2.10.6 Health-Related Quality of Life (HRQL) Total Score as Assessed by [REDACTED] (1-week recall)	FAS	Descriptive statistics, include CFB
14.2.11.1 [REDACTED] Domains	FAS	Include 5 domain categorical summaries: mobility, self-care, usual activities, pain/discomfort and anxiety/depression
14.2.11.2 [REDACTED] Crosswalk Index Value	FAS	Descriptive statistics, include CFB
14.2.11.3 [REDACTED] VAS Value	FAS	Descriptive statistics, include CFB and percent CFB
14.2.12.1 Overall Symptom Severity Bladder Symptoms Based on Patient Global Impression of [REDACTED] (PGI [REDACTED])	FAS	Let's try to include both continuous variables (score and change from baseline) and categorical variable on the same table which will facilitate review

Title	Population	Programming notes
14.2.12.2 Overall Symptom Control over Bladder Symptoms Based on Patient Global Impression of [REDACTED] (PGI-[REDACTED])	FAS	Repeat 14.2.12.1
14.2.12.3 Overall Symptom Frequency Based on Patient Global Impression of [REDACTED] (PGI-[REDACTED])	FAS	Repeat 14.2.12.1
14.2.12.4 Overall Urgency-Related Leakage over Bladder Symptoms Based on Patient Global Impression of [REDACTED] (PGI-[REDACTED])	FAS-I	Repeat 14.2.12.1
14.2.12.5 Overall Change of Bladder Symptoms Based on Patient Global Impression of [REDACTED] (PGI-[REDACTED])	FAS	Categorical summary
14.2.12.1 [REDACTED] Domain Scores and Overall Satisfaction Score	FAS	Include CFB
Safety Endpoints		
Adverse Events		
14.3.1.1 Overall Summary of Treatment Emergent Adverse Events	SAF	
14.3.1.2 Treatment Emergent Adverse Events by System Organ Class and Preferred Term	SAF	

Title	Population	Programming notes
14.3.1.3 Treatment-Related Treatment Emergent Adverse Events by Preferred Term	SAF	
14.3.1.4 Treatment-Emergent Adverse Events by Preferred Term and Maximum Intensity	SAF	
14.3.1.5 Treatment Emergent Adverse Events with Grade ≥ 3 by Preferred Term	SAF	
14.3.1.6 Treatment-Related Emergent Adverse Events with Grade ≥ 3 by Preferred Term	SAF	
14.3.1.7 Treatment-Emergent Adverse Events occurring in $\geq 2\%$ subjects of Vibegron Arm and Greater Than the Placebo by Preferred Term	SAF	
14.3.1.8 Serious Treatment Emergent Adverse Events by Preferred Term	SAF	
14.3.1.9 Treatment-Related Serious Treatment Emergent Adverse Events by Preferred Term	SAF	
14.3.1.10 Treatment Emergent Adverse Events Leading to Discontinuation from Study Treatment by Preferred Term	SAF	
14.3.1.11 Fatal TEAEs by Preferred Term	SAF	

Title	Population	Programming notes
14.3.1.12 Treatment Emergent Adverse Events of Special Interest by Preferred Term	SAF	
14.3.1.13 Treatment-Related Treatment Emergent Adverse Events of Special Interest by Preferred Term	SAF	
14.3.1.14 Non-Fatal Treatment-Emergent Adverse Events by Preferred Term	SAF	
14.3.1.15 Hypertension Treatment Emergent Adverse Events by Preferred Term, and Pre-Existing Hypertension	SAF	
14.3.1.16 Hypertension Treatment Emergent Adverse Events by Preferred Term, and Baseline Hypertension	SAF	
14.3.1.17 Listing of Deaths	SAF	
14.3.1.18 Listing of Treatment Emergent Serious Adverse Events	SAF	
14.3.1.19 Listing of Treatment Emergent Adverse Events Leading to Withdrawal or Interruption of Study Treatment	SAF	
14.3.1.20 Listing of TEAEs of Special Interest	SAF	
Safety Labs		
14.3.2.1 Hematology Laboratory Parameters	SAF	Include observed and CFB

Title	Population	Programming notes
14.3.2.2 Clinical Chemistry Laboratory Parameters	SAF	Include observed and CFB
14.3.2.3 Urinalysis Laboratory Parameters	SAF	Include observed and CFB
14.3.2.4 Summary of Other Laboratory Parameters	SAF	
14.3.2.5 Abnormal Classification of Hematology Laboratory Parameters	SAF	
14.3.2.6 Abnormal Classification of Clinical Chemistry Laboratory Parameters	SAF	
14.3.2.7 Abnormal Classification of Urinalysis Laboratory Parameters	SAF	
14.3.2.8 Abnormal Classification Summary of Other Laboratory Parameters	SAF	
14.3.2.9 Shift Table of L/N/H Classification for Hematology Laboratory Parameters	SAF	
14.3.2.10 Shift Table of L/N/H Classification for Chemistry Laboratory Parameters	SAF	
14.3.2.11 Maximum Post-baseline ALT and AST vs. Maximum Post-baseline Bilirubin	SAF	
14.3.2.12 Listing of Subjects who Potentially Met Hy's Law	SAF	

Title	Population	Programming notes
Concomitant Medication		
14.3.3.1 Non-OAB Concomitant Medication	SAF	
14.3.3.2 OAB Concomitant Medication	SAF	
Regular and Orthostatic Vital Signs		
14.3.4.1 Vital Sign Parameters	SAF	Include all observed and CFB
14.3.4.2 Vital Sign Parameter Change from Baseline Shifts at 3 Consecutive Visits	SAF	SBP, DBP and PR
14.3.4.3 Vital Sign Parameter Change from Baseline Shifts at Week 24	SAF	SBP, DBP and PR
14.3.4.4 Vital Sign Parameter Maximum Post-Baseline Change from Baseline	SAF	SBP, DBP and PR
14.3.4.5 Orthostatic Blood Pressure and Pulse Rate	SAF-Orth	
14.3.5.1 Time-Matched Change from Sitting to Standing Position in Orthostatic Blood Pressure and Pulse Rate	SAF-Orth	
14.3.5.2 Time-Matched Change from Day 1 in Orthostatic Blood Pressure and Pulse Rate	SAF-Orth	

Title	Population	Programming notes
14.3.5.3 Maximum CFB over 6 Hours in Orthostatic Blood Pressure and Pulse Rate	SAF-Orth	
14.3.5.4 Average CFB over 6 Hours in Orthostatic Blood Pressure and Pulse Rate	SAF-Orth	
14.3.5.5 Categorical Shift from Sitting to Standing in Blood Pressure	SAF-Orth	
Urodynamics		
14.3.6.1 Urodynamics Assessments	SAF-UDS	
Other		
14.3.7.1 Prostate Volume Measurements	SAF	
14.3.8.1 Uroflow Measurements	SAF	
14.3.9.1 Total IPSS score	SAF	
14.3.10.1 Physical Examination Shift from Baseline	SAF	

11.2.2. Output Figures

Table 10: List of Output Figures

Title	Population	Programming notes
Efficacy Endpoints		
14.2.1.1 Plot of LS Means (SE) of Change from Baseline in Average Number of Daily Micturition Episodes Primary Efficacy Analysis (MMRM)	FAS	Including all visits
14.2.1.2 Forest Plot of Vibegron Treatment Effect vs. Placebo on Average Number of Daily Micturition Episodes at Week 12 by Subgroup Primary Efficacy Analysis (MMRM)	FAS	
14.2.2.1 Plot of LS Means (SE) of Change from Baseline in Average Number of Daily Urgency Episodes Primary Efficacy Analysis (MMRM)	FAS	Including all visits
14.2.2.2 Forest Plot of Vibegron Treatment Effect vs. Placebo on Average Number of Daily Urgency Episodes at Week 12 by Subgroup Primary Efficacy Analysis (MMRM)	FAS	
14.2.3.1 Plot of LS Means (SE) of Change from Baseline in Average Number of Nocturia Episodes per Day (MMRM)	FAS	Including all visits
14.2.4.1 Plot of LS Means (SE) of Change from Baseline in Average Number of Daily Urge Urinary incontinence Episodes (MMRM)	FAS-I	Including all visits

Title	Population	Programming notes
14.2.5.1 Plot of LS Means (SE) of Change from Baseline in International Prostate Symptom Score (IPSS) Storage Score (MMRM)	FAS	Including all visits
14.2.6.1 Plot of LS Means (SE) of Change from Baseline in Volume Voided per Micturition (MMRM)	FAS	Including all visits
Safety Endpoints		
14.3.3.1 Scatter Plot of Maximum ALT Post-Baseline versus Maximum Total Bilirubin Expressed as Multiples of ULN	SAF	
14.3.3.2 Scatter Plot of Maximum AST Post-Baseline versus Maximum Total Bilirubin Expressed as Multiples of ULN	SAF	
14.3.3.3 Line Plot of Liver Chemistry Test Results over Time for Subjects with Elevated ALT or AST, and Elevated Total Bilirubin at Any Time	SAF	Only produce for subjects who potentially met Hy's law
14.3.4.1 Line Plot of Mean (SE) in CFB of Systolic Blood Pressure	SAF	X-axis starts from baseline visit
14.3.4.2 Line Plot of Mean (SE) in CFB of Diastolic Blood Pressure	SAF	X-axis starts from baseline visit
14.3.4.3 Line Plot of Mean (SE) in CFB of Pulse Rate	SAF	X-axis starts from baseline visit
14.3.5.1 Line Plot of Mean (SE) in Time-Matched Change from Day 1 of Orthostatic Systolic Blood Pressure	SAF-Orth	

Title	Population	Programming notes
14.3.5.2	Line Plot of Mean (SE) in Time-Matched Change from Day 1 of Orthostatic Diastolic Blood Pressure	SAF-Orth
14.3.5.3	Line Plot of Mean (SE) in Time-Matched Change from Day 1 of Orthostatic Pulse Rate	SAF-Orth
14.3.5.4	Empirical Cumulative Distribution Function of Maximum Change from Baseline over 6 Hours to Week 2 and Week 4 Orthostatic Systolic Blood Pressure	SAF-Orth Week 2 and Week 4 CDF plots side-by-side on the same page
14.3.5.5	Empirical Cumulative Distribution Function of Maximum Change from Baseline over 6 Hours to Week 2 and Week 4 Orthostatic Diastolic Blood Pressure	SAF-Orth Week 2 and Week 4 CDF plots side-by-side on the same page
14.3.5.6	Empirical Cumulative Distribution Function of Maximum Change from Baseline over 6 Hours to Week 2 and Week 4 Orthostatic Pulse Rate	SAF-Orth Week 2 and Week 4 CDF plots side-by-side on the same page

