If **any** of the following liver test abnormalities develop, study drug should be withheld immediately with appropriate clinical follow-up (including repeat laboratory tests, until a subject's laboratory profile has returned to normal/baseline status), and the event reported as an SAE:

- ALT or AST $> 8 \times$ upper limit of normal (ULN)
- ALT or AST $> 5 \times$ ULN and persists for more than 2 weeks
- ALT or AST $> 3 \times$ ULN and total bilirubin $> 2 \times$ ULN or international normalized ratio (INR) > 1.5
- ALT or AST $> 3 \times$ ULN with appearance of fatigue, nausea, vomiting, right upper quadrant pain or tenderness, fever, rash and/or eosinophilia ($> 5\%$)

Rechallenge may be considered if an alternative cause for the abnormal liver tests (ALT, AST, total bilirubin) is discovered and the laboratory abnormalities resolve to normal or baseline values. The investigator and Sponsor's designated Medical Monitor must discuss and agree with any decision to rechallenge.

Rechallenge should not occur when the etiology of the liver test abnormalities is considered possibly drug-induced.

8.4.6.2. Criteria for Permanent Discontinuation of Study Treatment in Association with Liver Test Abnormalities

Study treatment should be discontinued permanently if **all** of the following 4 criteria are met (ie, potential severe drug-induced liver injury/Hy's law case):

- Total bilirubin increases to $> 2 \times$ ULN or INR > 1.5 **and**
- AST or ALT increases to $\geq 3 \times$ ULN **and**
- Alkaline phosphatase value does not reach $2 \times$ ULN **and**

- No alternative cause explains the combination of the above laboratory abnormalities; important alternative causes include, but are not limited to the following:
 - Hepatobiliary tract disease
 - Viral hepatitis (eg, hepatitis A/B/C/D/E, Epstein-Barr virus)
 - Exposure to hepatotoxic agents/drugs or hepatotoxins, including herbal and dietary supplements, plants, and mushrooms
 - Alcoholic hepatitis
 - Non-alcoholic steatohepatitis
 - Autoimmune hepatitis

If an alternative cause for hepatotoxicity is identified, then it should be determined (based on the severity of the hepatotoxicity or event) whether study drug should be withheld or permanently discontinued as appropriate for the safety of the subject, following consultation with the Sponsor's designated Medical Monitor.

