10.2. Appendix 2: Clinical Laboratory Tests

The tests detailed in [Table 4](#) will be performed by the central laboratory chosen by the Sponsor. Subjects do not need to fast prior to laboratory testing. A sample for urinalysis (including microscopy for RBCs, WBCs, epithelial cells, and bacteria) and urine culture will be sent to the central laboratory only if the urine dipstick tests positive for the presence of leukocytes, nitrites, or blood cells. If a subject reports symptoms suggestive of a urinary tract infection at any visit, a urine dipstick should be performed as needed, and a sample will be sent out for urinalysis and culture, and sensitivity testing.

Table 4 Clinical Laboratory Tests

Hematology	Chemistry	Urinalysis ^a	Other
Hematocrit	Albumin	Blood	PSA ^d
Hemoglobin	Alkaline phosphatase	Glucose	Coagulation INR/PT/APTT ^e
Platelet count	ALT	Protein	
WBC (total and differential)	AST	Specific gravity	
RBC	Bicarbonate	Microscopic exam (RBCs, WBCs, epithelial cells, and bacteria)	
	Calcium	pH	
	Chloride	Color	
	Creatinine ^b		
	Glucose (fasting or non-fasting)		
	Potassium		
	Sodium		
	Total bilirubin		
	Direct bilirubin ^c		
	Blood urea nitrogen		
	Total cholesterol		

ALT = alanine aminotransferase; APTT = activated partial thromboplastin time; AST = aspartate aminotransferase; eGFR = estimated glomerular filtration rate; INR = international normalized ratio; PSA = prostate-specific antigen; PT = prothrombin time; RBC = red blood cell count; WBC = white blood cell count

^a A sample for urinalysis and urine culture/sensitivity will be sent to the central laboratory only if the urine dipstick performed at the site is positive for the presence of leukocytes, nitrites, or blood cells.

^b eGFR will be calculated and reported by the central lab.

^c If total bilirubin is elevated above the upper limit of normal.

^d PSA performed by central laboratory at Screening.

^e Only upon request from Principal Investigator (if ALT, AST and bilirubin are increased).

10.3. Appendix 3: Adverse Events: Definitions and Procedures for Recording, Evaluating, Follow-up, and Reporting

Definition of an AE

AE Definition

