All continuous laboratory parameters will be summarized descriptively by absolute value at each visit by treatment group, together with the corresponding changes from baseline. All parameters will be summarized in SI units.

The number and percentage of subjects with laboratory measurements outside of the central laboratory normal range will also be summarized by treatment group and visit. Shift tables from baseline to maximum post-baseline value, to minimum post-baseline value, last post-baseline value, and at each post-baseline visit will be provided for hematology and chemistry parameters to display low, normal, high, and missing values by treatment group in a 3-by-3 contingency table. Denominators for percentages will be the number of subjects with non-missing data at the specific assessment and baseline.

Maximum post-baseline total bilirubin will be presented (<2 and $\geq 2 \times$ ULN) and plotted against maximum post-baseline ALT (<3 , ≥ 3 - <5 , ≥ 5 - <10 , and $\geq 10 \times$ ULN), expressed as multiples of ULN. This will be repeated to show maximum post-baseline total bilirubin against maximum post-baseline AST.

Data for subjects with ALT or AST $\geq 3 \times$ ULN, and bilirubin $\geq 2 \times$ ULN will be presented, which will include all visits for this subset of subjects. A line plot of liver biochemistry test results (including ALP, ALT, AST, total bilirubin, and GGT) over time will also be presented for this subset of patients.

A sample for the urinalysis and urine culture will be sent to the central laboratory only if the urine dipstick performed at the site tests positive for the presence of leukocytes, nitrites, or blood cells. Dipstick results and central urinalysis data will be provided only in the listing.

Any data outside the central laboratory normal reference ranges will be explicitly noted on the listings that are produced.

7.3. **Vital Sign Assessments**

7.3.1. **Height, Weight, and Sitting Vital Signs**

Vital sign data including systolic and diastolic blood pressure, pulse rate, respiration rate, body temperature and weight will be collected at all study visits except for the safety follow-up visit. Height will be measured at Screening only. Blood pressure will be measured in triplicate at each

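### The SAP's Hy's law outputs select on bilirubin only, although the protocol's Hy's law case can also be met through INR above 1.5

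*SAP*

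**What the plan says.** **Protocol 8.4.6.2** sets four criteria, all required, for what it calls a "potential severe drug-induced liver injury/Hy's law case":

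1. "Total bilirubin increases to $> 2 \times$ ULN or INR > 1.5"
2. "AST or ALT increases to $\geq 3 \times$ ULN"
3. "Alkaline phosphatase value does not reach $2 \times$ ULN"
4. no alternative cause for the combination.

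**Protocol 10.2, Table 4** lists INR with the coagulation tests in its column of other tests. Footnote e limits when it is run: "Only upon request from Principal Investigator (if ALT, AST and bilirubin are increased". The footnote does not say how far each test must be raised. GGT is not in the table.

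**SAP 7.2** presents data for subjects with ALT or AST ≥ 3 × ULN and bilirubin ≥ 2 × ULN, and adds a line plot of liver tests for the same subset, "including ALP, ALT, AST, total bilirubin, and GGT".

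**SAP 11.2.2** titles that plot, Figure 14.3.3.3, "Line Plot of Liver Chemistry Test Results over Time for Subjects with Elevated ALT or AST, and Elevated Total Bilirubin at Any Time". Its programming note restricts it to subjects who potentially met Hy's law, so the SAP attaches that label to the ALT/AST-plus-bilirubin subset.

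**SAP 11.2.1** plans output 14.3.2.12, "Listing of Subjects who Potentially Met Hy's Law", with no criterion and no programming note.

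**The concern.** In the protocol, bilirubin and INR are alternatives. In the SAP, bilirubin is the only route. A screen for potential cases may reasonably be wider than the definition it serves, so that no case escapes and a clinician can judge the rest. On ALP and alternative cause the SAP is indeed wider than the protocol. On INR it is narrower.

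At stake is whether the two outputs named for Hy's law can be relied on to contain every man who meets the trial's own laboratory criteria. These events are rare, and a reader of such a listing mainly wants to know whether it is empty. Under the SAP rule it could be empty while a protocol-defined case exists elsewhere in the report.

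**Working it through.** The plan gives no figure to reproduce, so the check compares the two rules directly.

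**Rules** (values in × ULN except INR; no alternative cause is assumed present):

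- Protocol 8.4.6.2: (bilirubin > 2 or INR > 1.5) and (ALT or AST ≥ 3) and ALP < 2.
- SAP 7.2: (ALT or AST ≥ 3) and bilirubin ≥ 2.

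**Illustrative grid** (assumed values, chosen to straddle the thresholds): ALT or AST 2.9, 3.0, 3.5, 9; bilirubin 0.8, 1.0, 1.5, 2.0, 2.1; INR not done, 1.0, 1.5, 1.6; ALP 1.0, 2.0. This gives 4 × 5 × 4 × 2 = 160 combinations.

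**Counts.** Three transaminase values reach 3.

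- Protocol criteria met (ALP 1.0 only): bilirubin 2.1 with any INR entry gives 4; the other four bilirubin values with INR 1.6 give 4. Total 3 × (4 + 4) = 24.
- SAP rule met: 3 × 2 bilirubin values × 4 INR entries × 2 ALP values = 48.
- Both met: bilirubin 2.1 with any INR entry (4) plus bilirubin 2.0 with INR 1.6 (1), at ALP 1.0. Total 3 × 5 = 15.
- Protocol only: 24 − 15 = 9.
- SAP only: 48 − 15 = 33.

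All 9 protocol-only combinations have INR 1.6 and bilirubin below 2. One example is ALT 3.5, bilirubin 1.5, INR 1.6, ALP 1.0.

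**Can the case be observed?** If footnote e means that INR is run only when bilirubin is above ULN (with ALT and AST both raised), 3 of the 9 remain, all with bilirubin 1.5. The footnote sets no 2 × ULN floor for bilirubin, so the band between 1 and 2 × ULN stays open.

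**After the fix.** With (ALT or AST ≥ 3) and (bilirubin ≥ 2 or INR > 1.5), the number selected is 3 × 2 × (2 × 4 + 3 × 1) = 66. All 24 protocol combinations are among them, so none is missed. The other 66 − 24 = 42 are over-inclusive: the same 33 as before, plus 9 with ALP 2.0 selected through INR.

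These are counts of combinations, not frequencies in patients.

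**The case against.** **The man is not lost from the report.** This stands. Protocol 8.4.6.1 requires drug to be withheld and an SAE reported when ALT or AST exceeds 3 × ULN with INR above 1.5, and a transaminase elevation leading to withholding or discontinuation is an event of special interest. If treatment-emergent, he belongs in the serious event outputs (14.3.1.8, 14.3.1.18), the special-interest outputs (14.3.1.12, 14.3.1.20) and the withdrawal or interruption listing (14.3.1.19). His INR probably appears under other laboratory parameters (14.3.2.4, 14.3.2.8, 16.2.3.8), since Protocol Table 4 places it in that column. A reader might infer that a liver case would go unreported; the documents do not support that. None of these outputs, however, identifies him as a potential Hy's law case.

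**The listing's rule is inferred.** This also stands. Listing 14.3.2.12 gives no criterion. SAP 7.2 is the only rule a programmer is given, and the note to Figure 14.3.3.3 ties that rule to the Hy's law label.

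**A bilirubin-only screen is defensible, because INR depends on an investigator's request.** This is fair as far as it goes: an INR limb can only find men in whom INR was measured. It is no reason to ignore the result where one exists.

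**SAP Section 9 need not declare this.** A reader might take it for an undeclared departure from a planned analysis. Protocol 9.4.3 leaves the safety analysis to the SAP, Protocol 9.4.3.2 plans no Hy's law analysis, and 8.4.6.2 is a discontinuation criterion. Section 9 is not clearly engaged.

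**Conclusion.** The mismatch is real and narrow. As written, SAP 7.2 and Figure 14.3.3.3, and by inference Listing 14.3.2.12, can leave out a man who meets Protocol 8.4.6.2 through INR while his bilirubin is below 2 × ULN. In practice this mainly means bilirubin between 1 and 2 × ULN, INR requested and above 1.5, ALP below 2 × ULN and no other cause. Few of the planned 1088 men are likely to be affected, but that is a judgement: the documents give no rate.

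The conclusion assumes that the listing follows SAP 7.2 and that INR may be run once bilirubin is above ULN.

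A reader might also infer that a reported count of Hy's law cases would be wrong. The SAP plans a listing and a plot, not a count statement, so the finding concerns the completeness of those two outputs. Efficacy is unaffected. The correction is worth making because it costs one condition on data already collected.

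**What to change.** In SAP 7.2, Listing 14.3.2.12 and Figure 14.3.3.3:

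- Select men with ALT or AST ≥ 3 × ULN and (bilirubin ≥ 2 × ULN or INR > 1.5). Write this rule against the listing, which now has none.
- Describe it as a screen that covers every case meeting the laboratory criteria of Protocol 8.4.6.2. It will not reproduce that definition exactly, because it applies no ALP or alternative-cause condition and uses ≥ 2 rather than > 2 × ULN.
- Show INR (where measured) and ALP in the listing so that the remaining criteria can be judged case by case.
- In the plot, add INR and drop GGT, which Protocol Table 4 does not collect. ALP is already plotted.
- Amend the title of Figure 14.3.3.3 to match.

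The cost is one selection condition, one plotted parameter exchanged and two columns in a listing. No new data are needed and no treatment rule changes.
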